## 4. ELIGIBILITY CRITERIA

### 4.1 INCLUSION CRITERIA

**No waivers/exemptions will be granted for protocol inclusion/exclusion criteria.**

Subjects are included in the study if they meet all of the following criteria:

- Written informed consent provided by the patient.
- Male or female, age  $\geq 18$  years.
- For group A, patients must have received and failed anti-TNF therapy. For group B, subjects must not have received any prior treatment with any anti-TNF therapy.
- Patients who have received 200mg dose of bermekimab in this study are eligible to begin receiving 400mg dose starting with the patient's next scheduled visit for the remainder of his/her treatment plan.
- Diagnosis of HS for at least 1 year prior to screening.
- HS affecting at least two distinct anatomic areas, one of which is Hurley II or III stage.
- A total body count of abscesses and inflammatory nodules (AN) of at least 3
- Full understanding of the procedures of the study protocol and willingness to comply with them.
- In case of female patients of childbearing potential, willingness to use one method of contraception of high efficacy during the entire study period. This method can be hormonal contraceptives or one of the following: condoms, diaphragm, or an intrauterine device. Women of non-childbearing potential include those considered to have a medical history that indicates that pregnancy is not a reasonable risk, including post-menopausal women and those with a history of hysterectomy.

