## 8.2 Study Endpoints

The primary endpoint of this study is the safety and tolerability of bermekimab at 400 mg weekly subcutaneous dose.

The secondary endpoints include:

- Hidradenitis Suppurativa Clinical Response (HiSCR) score (baseline to visit 13). For this score patients are defined as achievers or non-achievers. The positive HiSCR score is defined as a  $\geq 50\%$  reduction in inflammatory lesion AN count (sum of abscesses and inflammatory nodules), and no increase in abscesses or draining fistulas in HS compared with the lesions counted on visit 1. The HiSCR score, including inflammatory lesion count, will be measured on visits 1, 3, 5, 7, 9, 11, 13 and 14.
- Pharmacokinetics (PK) (baseline to visit 13). An enzyme-linked immunosorbent assay (ELISA) has been developed to specifically measure bermekimab levels in human plasma. Blood will be drawn into a single 6 ml collection tube at each PK collection time point (sample collection is pre-dose at visit 1, visit 3, visit 5, visit 9 and visit 13). These samples will be collected per the study lab manual and immediately shipped to the Sponsor for PK analysis. The PK samples will also be used to test for the presence of antibodies against bermekimab.
- Physician's Global Assessment (PGA) (baseline to visit 13). This is defined as: a) clear when the total number of abscesses is 0, the total number of draining fistulas is 0, the total number of inflammatory nodules is 0 and the total number of non-inflammatory nodules is 0; b) minimal when the total number of abscesses is 0, the total number of draining fistulas is 0, the total number of inflammatory nodules is 0 and there is presence of non-inflammatory nodules; c) mild when the total number of abscesses is 0, the total number of draining fistulas is 0, and the total number of inflammatory nodules is 1-4, or when there is presence of one abscess or draining fistula and absence of any inflammatory nodules; d) moderate when the total number of abscesses is 0, the total number of draining fistulas is 0 and the total number of inflammatory nodules is at least 5; or when there is presence of one abscess or draining fistula and at least one inflammatory nodule; or when there are 2-5 abscesses or draining fistulas and fewer than 10 inflammatory nodules; e) severe when the total number of abscesses or draining fistulas is 2-5 and the total number of inflammatory nodules is at least 10; and f) very severe when there

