are more than 5 abscesses or draining fistulas. The PGA will be measured on visits 1, 3, 5, 7, 9, 11, 13 and 14.

- Disease Activity Score (baseline to visit 13). This is defined as the sum of scores of all affected areas of each patient. Each area will be evaluated by the following formula: (multiplication of the two largest diameters in each affected area in mm) x (the degree of inflammation of each lesion). This score has been proposed by our study group. The Disease Activity Score will be measured on visits 1, 3, 5, 7, 9, 11, 13 and 14.
- The modified Sartorius score (baseline to visit 13). The Sartorius Scale is used to quantify the severity of HS. Points are awarded for 12 body areas (left and right axillae, left and right sub/inframammary areas, intermammary area, left and right buttocks, left and right inguino-crural folds, perianal area, perineal area, and other): points were awarded for nodules (2 points for each); abscesses (4 points); fistulas (4 points); scars (1 point); other findings (1 point); and longest distance between two lesions (2-6 points, 0 if no lesions); and if lesions are separated by normal skin (yes-0 points; no-6 points). The total Sartorius score is the sum of the 12 regional scores. The modified Sartorius score will be measured on visits 1, 3, 5, 7, 9, 11, 13 and 14.
- Change in AN count (baseline to visit 13). The sum of abscesses and inflammatory nodules for each patient will be measured on visits 1, 3, 5, 7, 9, 11, 13 and 14.
- Change in VAS for Disease Severity and Pain (baseline to visit 13). Patient reported visual analogue scales for pain and disease severity will be measured on visits 1, 3, 5, 7, 9, 11, 13 and 14.
- Change in Dermatology Life Quality Index (DLQI) (baseline to visit 13). This will be measured on visits 1, 3, 5, 7, 9, 11, 13 and 14.
- Change in Hospital Anxiety Depression Scale (HADS) (baseline to visit 13). This will be measured on visits 1, 3, 5, 7, 9, 11, 13 and 14.

Changes in secondary endpoints will be presented by individual cohort, as well as combined across both cohorts.

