## **10. STATISTICAL PLAN**

This section provides the basis for the statistical analysis plan (SAP) for the study. The SAP may be revised during the study to accommodate amendments to the clinical study protocol, and to make changes to adapt to unexpected issues in study execution and data that may affect planned analyses. Analysis variables are listed in Section 8.

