#### **10.5.3 Analysis of Secondary Endpoints:**

Proportion of patients achieving a positive Hidradenitis Suppurativa Clinical Response (HiSCR) score after 13 weeks will be summarized by treatment group (and pooled overall population). The corresponding 95% confidence interval (CI) for the point estimate will be provided. Subjects previously enrolled in the 200mg/weekly dosing cohort who have received *two or fewer* bermekimab injections (2 x 200mg doses) before beginning the 400mg weekly doses will be included for data analysis together with those receiving all doses at 400mg/weekly. Patients who have received more than 2 bermekimab injections of 200mg may enter the 400mg/week arm; however, only patients who have received *two or fewer* bermekimab injections will be included in the data analysis.

Change in outcomes from baseline to week 13 (VAS for disease, VAS for pain, DLQI, inflammatory lesion count, PGA, Disease Activity Score, and modified Sartorius score) will be summarized using descriptive statistics (n, mean, standard deviation, median, minimum and maximum value). The 95% CI of the mean change from baseline will be provided.

A rank-ordered analysis will be performed for the total abscess and inflammatory nodule count (ranked at 0, 1 or 2) and reduction in pain score (categorized as  $\geq 30\%$  reduction on pain score among patients with baseline score of  $\geq 3$ ). The change in modified Sartorius score will be dichotomized at 4 ( $\leq 4$  least severe disease, higher indicates severe disease). Number and percent under each treatment group (and pooled overall) will be summarized.

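### Section 10.5.3 cuts the change in modified Sartorius score at 4 but names the classes as disease severity, so unchanged and slightly worse patients count as 'least severe'

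*Combined protocol and SAP*

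**What the plan says.** The combined protocol and SAP, Section 10.5.3, states: "The change in modified Sartorius score will be dichotomized at 4". The bracket that follows assigns values of 4 or less to "least severe disease, higher indicates severe disease". Number and percent are to be reported for each group and pooled.

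Section 8.2 describes the instrument: "The Sartorius Scale is used to quantify the severity of HS", and "The total Sartorius score is the sum of the 12 regional scores". Its item points include 2 for each nodule, 4 for abscesses and 4 for fistulas.

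Section 10 says "Analysis variables are listed in Section 8". Section 8 gives no cut of 4 for the modified Sartorius score, neither for the score nor for its change. Section 10.5.3 does not say which value is subtracted from which.

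**The concern.** The variable in the rule is a change, but the class names describe a level of disease. A change of 0 is compatible with any level, so the names do not follow from the variable.

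The rule produces a percentage by group and pooled, in an open-label study with no control group and a planned 20 patients. A reader of the table would naturally take the percentage with least severe disease as a treatment result. If all 10 patients of a group are analysed, each one moves that percentage by 1/10 = 10 points, and the pooled percentage by 1/20 = 5 points.

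**Working it through.** The plan attaches no sample size, power or test to this analysis, so there is no figure of its own to reproduce. The check applies the rule as written in both directions. Let b be the visit-1 score and f the visit-13 score.

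**Inputs.** Cut and class names: Section 10.5.3. Item points: Section 8.2 (nodule 2, abscess 4, fistula 4). HiSCR definition: Section 8.2. The score pairs below are illustrations; none comes from the documents.

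**Direction A: change = f − b.** A patient is 'least severe' if f − b ≤ 4, that is, if f ≤ b + 4. The working cut on the visit-13 score is therefore b + 4 and differs by patient.
- 60 to 60: change 0, 'least severe'.
- 60 to 64: change +4, 'least severe'.
- 60 to 65: change +5, 'severe'.
- 20 to 25: change +5, 'severe', although the patient at 64 has 64/25 = 2.56 times this score and is 'least severe'.
- 50 to 60: change +10, 'severe', although the patient who stays at 60 ends at the same score and is 'least severe'.

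**Direction B: change = b − f.** A patient is 'least severe' if b − f ≤ 4.
- 60 to 60: change 0, 'least severe'.
- 60 to 64: change −4, 'least severe'.
- 60 to 90: change −30, 'least severe'.
- 60 to 55: change 5, 'severe'.
- 60 to 20: change 40, 'severe'.

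Under both directions, a patient who is unchanged or 1 to 4 points worse is 'least severe'. Under B, every worsened patient is 'least severe', and every improvement of more than 4 points is 'severe'.

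**Against the plan's own response measure.** One new abscess with other items unchanged adds 4 points, so under either direction the patient is 'least severe'. HiSCR requires "no increase in abscesses or draining fistulas in HS compared with the lesions counted on visit 1" together with a 50% reduction in the abscess and inflammatory nodule (AN) count. The same patient has one more abscess and no reduction, and is a non-achiever.

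**How many patients.** The documents give no spread for the change, so this part rests on an assumption. Suppose no true mean change, whole-number scores and a normal distribution. The share labelled 'least severe' is then Φ(4.5/SD):
- SD 5: Φ(0.90) = 82%.
- SD 10: Φ(0.45) = 67%.
- SD 20: Φ(0.225) = 59%.

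By symmetry, the shares are the same under direction B. Across this assumed range, most patients would carry the favourable label when the group as a whole had not changed.

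**The case against.** **It is an obvious slip.** The class names fit a level, so a reader could take 4 as a cut on the visit-13 score and move on. That the sentence is a slip is likely; which word is wrong is not known. The sponsor may have meant a change with the wrong class names, or a score with a stray word. Nothing in Section 8 settles it.

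**Eligibility shows that the score was meant.** A reader might infer that no patient can start at 4 or less, so the cut can only concern the score. Entry requires "A total body count of abscesses and inflammatory nodules (AN) of at least 3", and three nodules at 2 points give 3 × 2 = 6. That floor holds only if the count is present at visit 1. The criterion names no visit, the screening procedures list no lesion count, and screening may be up to 21 days before visit 1. Even with a firm floor, the sponsor's intention would not follow from it.

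**Putting the cut on the score cures it.** It does so only if the class names go too. Three inflammatory nodules with no abscess or fistula score at least 6, which is above 4 and so 'severe'. The Physician's Global Assessment in Section 8.2 calls that patient mild (1 to 4 inflammatory nodules).

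**The SAP can still be revised.** Section 10 does allow revision. However, it does not defer this rule, whereas Section 10.5.5 expressly leaves its exposure periods to the SAP. A programmer who follows Section 10.5.3 produces the mislabelled table, and one who silently corrects it departs from the plan.

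**The stakes are low.** This stands. It is one descriptive count of a secondary endpoint in a convenience sample, with no formal test of the primary endpoint.

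**Conclusion.** The rule is wrong as written. It applies severity names to a change, and no choice of direction makes them fit. Unchanged patients and those up to 4 points worse are counted as 'least severe' under either direction; under visit 1 minus visit 13, so is every other worsened patient, while improvements of more than 4 points become 'severe'.

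These statements need only the text of Section 10.5.3. The abscess example also uses the 4 points in Section 8.2 and assumes that no other item moves. The shares of 59% to 82% depend on the assumed distribution and are not forecasts for this trial.

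A reader might infer that the trial's efficacy reporting as a whole is compromised. The documents do not support that: safety, HiSCR and the mean Sartorius change with its 95% confidence interval are defined separately and are unaffected. The damage is limited to one descriptive table, by group and pooled.

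**What to change.** Any one of three changes is enough.

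1. Delete the dichotomy and rely on the mean change with 95% confidence interval already planned in Section 10.5.3. This is the simplest.
2. Keep the cut on the change, define it as the visit-13 score minus the visit-1 score, and name the classes by change: *increase of more than 4 points* versus *decrease, no change, or increase of 4 points or less*.
3. If the sponsor confirms that 4 was meant for the score, apply it to the visit-13 score and report *4 or less* and *more than 4*, without the word severe.

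Under options 2 and 3, name the visit. Section 8.2 uses visit 13 (day 84), Section 10.5.3 says week 13, and the score is also taken at visit 14 (day 91, which is 91/7 = 13 weeks).

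A minor addition in the same paragraph: the AN count is ranked at 0, 1 or 2. If these are counts rather than rank codes, add a level *3 or more* at visit 13, so that every analysed patient with a count has a level. A patient going from 6 to 3 meets the 50% reduction part of HiSCR but would otherwise have none.

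The cost is one sentence and at most one table row. The scores and counts are already collected at visits 1 and 13, so no new data or visits are needed.

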#### **10.5.4 Pharmacodynamics (PK) analysis:**

Descriptive statistics of PK parameters will be presented in a table format. The summary will include average bermekimab concentration at visit cycles along with the standard deviation and coefficient of variation (CV).

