## Visit 3 (day 14 +/-2):

- ***At least 45 minutes before injection:*** Remove syringe from refrigeration and lay flat; allow to warm to room temperature. Do not heat
- Pre-injection
  - Physical Exam
  - DLQI
  - Urine pregnancy
  - HISCR
  - PGA
  - Disease Activity Score
  - Modified Sartorius
  - HADS
  - VAS for disease
  - VAS for pain
  - Vital signs (blood pressure, pulse, oxygen saturation, respiratory rate and body temperature)
  - Blood draw for chemistry, hematology, CRP, ESR and blood draw for PK and biomarker analysis
- Bermekimab subcutaneous injection, in accordance with injection site determined by BMI at Screening
- 1 hour monitoring for injection reaction
- Vital signs (blood pressure, pulse, oxygen saturation, respiratory rate and body temperature) one hour post injection (70 +/- 10 minutes)
- Adverse event monitoring
- Concomitant medications/treatments

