### **5.5 PATIENT CROSSOVER RULES**

Patients enrolled in the 200mg dose study are eligible to receive 400mg bermekimab injections upon consent to this protocol. Upon consent, patients will begin 400mg bermekimab dosing at next Study Day Visit, following patient calendar so that total number of bermekimab injections, 200mg + 400mg, is equal to 13 at end of study.

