## 6. CORRELATIVE STUDIES

### 6.1 PHARMACOKINETICS (PK) SAMPLE COLLECTION

An enzyme-linked immunosorbent assay (ELISA) has been developed to specifically measure bermekimab levels in human plasma. Blood will be drawn into a single 6 ml collection tube at each PK collection time point (sample collection is pre-dose at visit 1, visit 3, visit 5, visit 9 and visit 13). These samples will be collected per the study lab manual and immediately shipped to the Sponsor for PK analysis. The PK samples will also be used to test for the presence of antibodies against bermekimab.

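### The PK summary is by visit with no split by dose history, so the visit 3 mean, and to a lesser degree the visit 5 mean, can mix 200 mg with 400 mg troughs

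*Combined protocol and SAP*

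**What the plan says.** PK is a listed secondary endpoint (synopsis, 3.1 and 8.2). Section 6.1 fixes the sampling times: "sample collection is pre-dose at visit 1, visit 3, visit 5, visit 9 and visit 13". Section 10.5.4 gives the whole analysis: "The summary will include average bermekimab concentration at visit cycles along with the standard deviation and coefficient of variation (CV". It names no dose, dose cohort, analysis population or listing.

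Section 5.5 lets patients from the 200 mg stage change dose: "Upon consent, patients will begin 400mg bermekimab dosing at next Study Day Visit". The same section keeps them on their existing schedule and counts the earlier doses: "following patient calendar so that total number of bermekimab injections, 200mg + 400mg, is equal to 13 at end of study". The visit numbering therefore carries on through the switch.

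Section 10.5.3 says that subjects with no more than two 200 mg injections "will be included for data analysis together with those receiving all doses at 400mg/weekly". Of the others it says "Patients who have received more than 2 bermekimab injections of 200mg may enter the 400mg/week arm", but it leaves them out of the data analysis.

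Section 10.5 summarises continuous data by treatment group. Groups A and B are defined by anti-TNF history, and both receive 400 mg weekly (synopsis, 2.5).

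**The concern.** A pre-dose concentration depends directly on the doses given before the sample. Pooling patients with slightly different early dosing may be tolerable for a clinical response judged at visit 13. It is not tolerable for a trough taken one week after the last 200 mg injection.

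Followed as written, the plan can produce a visit 3 mean, SD and CV that describe neither 200 mg nor 400 mg. Section 1.2 presents the study as dose ranging of the subcutaneous formulation, meant to prepare later randomised studies. The early troughs are part of the exposure evidence for that purpose. A mean that is low at visit 3 and nearly correct at visit 13 would also make the rise over time look steeper than it is at 400 mg. Section 10.5.4 promises no PK listing, so a reader of the report could not undo the mixing.

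**Working it through.** The plan states no PK figure to reproduce. The check traces which doses precede each sample and then sizes the effect under stated assumptions.

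**Dose trace (documents only).** Visit 3 is headed "Visit 3 (day 14 +/-2" and comes after the injections at visits 1 and 2. Its PK draw is listed before its injection.

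| 200 mg injections before switching | Doses before the visit 3 sample | Doses before the visit 5 sample |
|---|---|---|
| 0 | 400, 400 | 400 × 4 |
| 1 | 200, 400 | 200, then 400 × 3 |
| 2 | 200, 200 | 200 × 2, then 400 × 2 |

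The visit 1 sample precedes all dosing and is unaffected. The two-injection patient's visit 3 sample reflects 200 mg only. This step needs no kinetic assumption.

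**Size for one patient.** Assumptions, none of them in the documents: linear kinetics, exact weekly dosing, one-exponential carry-over q = 2^(−7/half-life), and a half-life of 7 to 28 days (q = 0.500 to 0.841). With n = visit number − 1 prior doses, the trough is proportional to the sum of doseᵢ × q^(n−i+1), for i = 1 to n. The ratio to an all-400 mg patient is:

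- after two 200 mg doses: 1 − 0.5(qⁿ + qⁿ⁻¹)/(q + q² + … + qⁿ)
- after one 200 mg dose: 1 − 0.5qⁿ/(q + q² + … + qⁿ)

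At visit 3, n = 2, so the two-dose ratio is 1 − 0.5(q² + q)/(q + q²) = 0.50 whatever q is. At visit 5 with a 7-day half-life it is 1 − 0.5(0.0625 + 0.125)/0.9375 = 0.90. With 28 days it is 1 − 0.5(0.500 + 0.595)/2.643 = 0.793.

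| Half-life (days) | Two 200 mg: V3 | V5 | V9 | V13 | One 200 mg: V3 | V5 |
|---|---|---|---|---|---|---|
| 7 | 0.500 | 0.900 | 0.994 | 1.000 | 0.833 | 0.967 |
| 14 | 0.500 | 0.833 | 0.967 | 0.992 | 0.793 | 0.931 |
| 21 | 0.500 | 0.807 | 0.945 | 0.980 | 0.779 | 0.914 |
| 28 | 0.500 | 0.793 | 0.931 | 0.970 | 0.772 | 0.905 |

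**Size for the visit 3 summary.** Suppose k of the 20 patients had two 200 mg doses and the rest only 400 mg. With f = k/20, the mean ratio is m = 1 − f/2 = 1 − k/40. If the within-dose CV is c in both sets, the variance in units of the squared 400 mg mean is c²(1 − 0.75f) + 0.25f(1 − f). The apparent CV is its square root divided by m.

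| k of 20 (assumed) | Mean relative to 400 mg | Apparent CV if true CV is 30% | If 50% |
|---|---|---|---|
| 0 | 1.000 | 30% | 50% |
| 1 | 0.975 | 32% | 52% |
| 2 | 0.950 | 34% | 53% |
| 5 | 0.875 | 40% | 57% |
| 10 | 0.750 | 46% | 62% |

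The CV rises in every mixed case. The SD rises only while 1 − f > 3c²: for a 30% CV, up to a crossover share of 73%; for a 50% CV, up to 25%, beyond which it falls.

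**Visit 5.** The mean is low by (k/20) × 0.10 to 0.207. With k = 5 that is 2.5% to 5.2%, against 12.5% at visit 3.

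**The case against.** The strongest reply is that this treats silence as a rule. Section 10.5.4 does not say that dose is ignored and does not label the summary as 400 mg. Section 10 calls itself the basis for a SAP that may be revised. Section 10.3.1 analyses the safety set as treated, and 10.5.2.2 summarises vital signs by dose cohort. The pooling rule stands among the HiSCR text of 10.5.3, not in the PK section. This stands in part: applying that rule to PK is an inference from PK being a secondary endpoint. The other reading does not help, though. If the rule does not reach PK, nothing excludes patients with more than two 200 mg injections. Their visit 3 samples are also 200 mg only, and after four such injections so is the visit 5 sample. The by-cohort presentation in 8.2 does not separate the samples either, because 10.5.3 puts patients with one or two 200 mg doses with the 400 mg patients.

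Second, the number of crossovers is unknown and the bias may be small or nil. This stands. With k = 2 the visit 3 mean is 5% low, while at an assumed 30% CV the standard error of a mean of 20 is 30%/√20 = 6.7%. PK here is descriptive, in a convenience sample, and could be re-tabulated later.

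Three stronger readings are tempting and lack support. A reader might infer that all the trial's exposure data are compromised, but visits 9 and 13 are little affected by patients with one or two 200 mg doses. A reader might infer that these patients enter every analysis population; the per-protocol set in 10.3.1 requires the baseline and visit 13 assessments, so one who leaves early is not in it, and no PK population is defined. A reader might also infer a biased accumulation analysis, but the plan contains none; the risk lies only in comparing the visit means.

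**Conclusion.** The point holds, limited to visit 3 and, to a lesser degree, visit 5. The plan expressly provides for patients with one or two 200 mg injections, directs that they be analysed with the 400 mg patients, and gives a PK summary that does not separate them. That a two-injection patient's visit 3 sample is a 200 mg trough follows from the documents alone. The 50% ratio needs linear kinetics. The ranges of 79-90% at visit 5, 93-100% at visit 9, at least 97% at visit 13, and 77-83% at visit 3 after a single 200 mg dose also need the assumed half-life of 7 to 28 days.

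The visit 3 mean is low by k/40 for k of 20 such patients, with the CV inflated and the SD usually so. No value of k can be taken from the documents, so no particular percentage should be quoted as the bias; it is zero if k is zero. The change is worth making because the defect is specific and cheap to remove, not because the distortion is known to be large.

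**What to change.** In 10.5.4:

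- State whether the two-or-fewer rule of 10.5.3 applies to PK.
- At visits 3 and 5, tabulate mean concentration, SD and CV by number of 200 mg injections received before the sample (0, 1, 2 or more). Base the 400 mg trough at those visits on patients whose earlier doses were all 400 mg.
- At visits 9 and 13, keep the pooled summary for patients with two or fewer 200 mg injections, and add an all-400 mg-only summary as a sensitivity check. Using only all-400 mg patients throughout would discard crossover patients where the distortion is small.
- List concentrations by patient with dose history.

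Sampling and treatment do not change, and the dosing dates and quantities are already recorded (11.9). The cost is smaller cells at visits 3 and 5, in a study of 20, plus one more table and one listing.
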